12. PUBLICATION POLICY

All information concerning vidutolimod and cemiplimab, Sponsor operations, patent application, formulas, manufacturing processes, basic scientific data, and formulation information, supplied by the Sponsor or its representatives to the Investigator and not previously published, is confidential and remains the sole property of the Sponsor. The Investigator agrees to use this information only to complete this study and not for other purposes without the Sponsor written consent.

The institution and Investigator understand that the information developed in this study will be used by the Sponsor in connection with the continued development of vidutolimod and cemiplimab, and thus may be disclosed as required to other Investigators, government regulatory agencies, or other scientific groups. To permit the information derived from this study to be used, the Investigator is obligated to provide the Sponsor with all data obtained in the study.

13. APPENDICES

APPENDIX A. VIDUTOLIMOD INJECTION GUIDELINES

Refer to Section 4.1.1.3. Vidutolimod Injections and the current Intratumoral and Pharmacy Manual for tumor selection and additional information.

[figure not shown]
Method of Vidutolimod Administration

Intratumoral Injection

Using standard aseptic technique, the needle should be inserted near the tumor periphery ([Appendix Figure 1](#) left panel) and advanced into the tumor to the desired depth while maintaining gentle backward pressure on the syringe plunger to confirm an extravascular location of the needle tip. The syringe and needle should be slowly withdrawn to within a few millimeters of the skin or tumor surface while maintaining gentle downward pressure on the plunger to inject the desired volume of vidutolimod along the needle track ([Appendix Figure 1](#) middle panel).

With the tip of the needle still under the skin, the syringe should be rotated by ~20° to 40° and the process of insertion and injection during needle withdrawal repeated ([Appendix Figure 1](#) right panel). Using this process, vidutolimod is injected IT along multiple tracks through a single insertion point as far as the radial reach of the needle allows within the tumor; 2 insertion points may be used if the tumor is larger than the radial reach of the needle or the intended volume cannot be delivered through a single insertion point. If gentle injection pressure along 5 needle tracks within the tumor has not succeeded in delivering the desired volume, then the remainder of the vidutolimod may be injected peritumorally around the same lesion.

Appendix Figure 1: Method for Vidutolimod Intratumoral Injection

Recommended Intratumoral Injection Volume Based on Lesion Size

Lesion Size (longest dimension)	Vidutolimod Injection Volume
< 0.5 cm	Up to 0.25 mL
0.5 to 1.5 cm	Up to 0.5mL
1.5 to 2.5 cm	Up to 1 mL
> 2.5 cm	2 mL

Note: 2 mL is the maximum vidutolimod injection volume allowed in up to 3 accessible lesion(s) regardless of the lesion size. If the accessible lesion(s) cannot accommodate the full 2 mL volume, then the remaining volume may be injected peritumorally.

If the full volume cannot be injected within the tumor, the remaining drug volume should be injected into a second accessible tumor, if present; otherwise, the remaining volume should be injected SC near an original tumor (peritumoral). Vidutolimod dose should remain unchanged during the study.

Additional Guidance on Imaging Guided Injection of Vidutolimod

See Intratumoral Injection Manual

Subcutaneous Injection

[figure not shown]
SC administration of Vidutolimod should only occur when all accessible lesions have regressed. vidutolimod SC can be administered within the area of lymphatic drainage corresponding to the site of metastatic disease and follow local standards for SC injection.

In order to maximize the distribution and exposure to vidutolimod, the full volume from a single dose should be distributed to as many SC sites as is practical. It is recommended that equal amounts of drug be injected at each SC site.

Preferred sites of injection include the following (see also [Appendix Figure 2](#)):

- Location of the primary tumor.
- Within the area of lymphatic drainage corresponding to the site of metastatic disease. For example, in a subject with a muscle or bone metastasis in the lower leg, preferred SC injection sites would be in the same leg, with the expectation that at least some of the vidutolimod will drain to lymph nodes that also contain tumor antigens. Likewise, in a subject with metastases in an upper lobe of the lung, a preferred SC injection site would be in the ipsilateral supraclavicular fossa, where the injection may activate pDC in the supraclavicular lymph nodes that also can drain the upper lung.
- Unsuitable sites for injection would include, for example, the palm of the hand or the sole of the foot.

Appendix Figure 2: Preferred Sites of Subcutaneous Injection

APPENDIX B. RESPONSE EVALUATION CRITERIA IN SOLID TUMORS (RECIST)

Response Evaluation Criteria in Solid Tumors: RECIST (Version 1.1)

For the purposes of this study, patients should be re-evaluated for response every 9 weeks.

Response and progression will be evaluated in this study using the international criteria proposed by the revised Response Evaluation Criteria in Solid Tumors (RECIST) guideline (version 1.1; ([Eisenhauer, 2009](#))). Changes in the largest diameter (unidimensional measurement) of the tumor lesions and the short axis in the case of malignant lymph nodes are used in the RECIST criteria.

Selection of Lesions

- **Measurable disease:** Measurable lesions are defined as those that can be accurately measured in at least one dimension (longest diameter to be recorded) as ≥ 20 mm (≥ 2 cm) by chest x-ray or as ≥ 10 mm (≥ 1 cm) with axial CT scan, MRI, or calipers by clinical exam. All tumor measurements must be recorded in millimeters (or decimal fractions of centimeters).
- **Malignant lymph nodes:** To be considered pathologically enlarged and measurable, a lymph node must be ≥ 15 mm (≥ 1.5 cm) in short axis when assessed by CT scan (CT scan slice thickness recommended to be no greater than 5 mm [0.5 cm]). At baseline and in follow-up, only the short axis will be measured and followed.
- **Non-measurable disease:** All other lesions (or sites of disease), including small lesions (longest diameter <10 mm [<1 cm] or pathological lymph nodes with ≥ 10 to <15 mm [≥ 1 to <1.5 cm] short axis), are considered non-measurable disease. Bone lesions, leptomeningeal disease, ascites, pleural/pericardial effusions, lymphangitis cutis/pulmonitis, inflammatory breast disease, and abdominal masses (not followed by CT or MRI), are considered as non-measurable.

Note: Cystic lesions that meet the criteria for radiographically defined simple cysts should not be considered as malignant lesions (neither measurable nor non-measurable) since they are, by definition, simple cysts. ‘Cystic lesions’ thought to represent cystic metastases can be considered as measurable lesions, if they meet the definition of measurability described above. However, if non-cystic lesions are present in the same patient, these are preferred for selection as target lesions.

- **Target lesions:** All measurable lesions up to a maximum of 2 lesions per organ and 5 lesions in total, representative of all involved organs, should be identified as target lesions and recorded and measured at baseline. Target lesions should be selected on the basis of their size (lesions with the longest diameter), be representative of all involved organs, but in addition should be those that lend themselves to reproducible repeated measurements. It may be the case that, on occasion, the largest lesion does not lend itself to reproducible measurement in which circumstance the next largest lesion which can be measured reproducibly should be selected. A sum of the diameters (longest for non-nodal lesions, short axis for nodal lesions) for all target lesions will be calculated and reported as the baseline sum diameters. If lymph nodes are to be included in the sum, then only the short axis is added into the sum. The baseline sum diameters will be

used as reference to further characterize any objective tumor regression in the measurable dimension of the disease.

- **Non-target lesions:** All other lesions (or sites of disease) including any measurable lesions over and above the 5 target lesions should be identified as non-target lesions and should also be recorded at baseline. Measurements of these lesions are not required, but the presence, absence, or in rare cases unequivocal progression of each should be noted throughout follow-up.

Methods for Evaluation of Measurable Disease

All measurements should be taken and recorded in metric notation using a ruler or calipers. All baseline evaluations should be performed as closely as possible to the beginning of treatment and never more than 4 weeks before the beginning of the treatment.

The same method of assessment and the same technique should be used to characterize each identified and reported lesion at baseline and during follow-up. Imaging-based evaluation is preferred to evaluation by clinical examination unless the lesion(s) being followed cannot be imaged but are assessable by clinical exam.

- **Color Photography.** Clinical lesions will only be considered measurable when they are superficial (eg, skin nodules and palpable lymph nodes) and ≥ 10 mm (≥ 1 cm) diameter as assessed using calipers (e.g., skin nodules). In the case of skin lesions, documentation by color photography, including a ruler visible in each image to estimate the size of the lesion, is required. (NOTE: Radiologic imaging should be used for lymph nodes)
- **Chest x-ray.** Lesions on chest x-ray are acceptable as measurable lesions when they are clearly defined and surrounded by aerated lung. However, CT is preferable.
- **Conventional CT and MRI.** This guideline has defined measurability of lesions on CT scan based on the assumption that CT slice thickness is 5 mm (0.5 cm) or less. If CT scans have slice thickness greater than 5 mm (0.5 cm), the minimum size for a measurable lesion should be twice the slice thickness. MRI is also acceptable in certain situations.
- **PET-CT.** At present, the low dose or attenuation correction CT portion of a combined PET-CT is not always of optimal diagnostic CT quality for use with RECIST measurements. However, if the site can document that the CT performed as part of a PET-CT is of identical diagnostic quality to a diagnostic CT (with IV and oral contrast), then the CT portion of the PET-CT can be used for RECIST measurements and can be used interchangeably with conventional CT in accurately measuring cancer lesions over time. Note, however, that the PET portion of the CT introduces additional data which may bias an investigator if it is not routinely or serially performed.
- **Ultrasound.** Ultrasound is not useful in assessment of lesion size and should not be used as a method of measurement. Ultrasound examinations cannot be reproduced in their entirety for independent review at a later date and because they are operator dependent, it cannot be guaranteed that the same technique and measurements will be taken from one assessment to the next. If new lesions are identified by ultrasound in

the course of the study, confirmation by CT or MRI is advised. If there is concern about radiation exposure at CT, MRI may be used instead of CT in selected instances.

- **Endoscopy, Laparoscopy.** The utilization of these techniques for objective tumor evaluation is not advised. However, such techniques may be useful to confirm complete pathological response when biopsies are obtained or to determine relapse in trials where recurrence following complete response (CR) or surgical resection is an endpoint.
- **Tumor markers.** Tumor markers alone cannot be used to assess response. If markers are initially above the upper normal limit, they must normalize for a patient to be considered in complete clinical response.
- **Cytology, Histology.** These techniques can be used to differentiate between partial responses (PR) and complete responses (CR) in rare cases (eg, residual lesions in tumor types, such as germ cell tumors, where known residual benign tumors can remain).
- The cytological confirmation of the neoplastic origin of any effusion that appears or worsens during treatment when the measurable tumor has met criteria for response or stable disease is mandatory to differentiate between response or stable disease (an effusion may be a side effect of the treatment) and progressive disease.
- **FDG-PET.** While FDG-PET response assessments need additional study, it is sometimes reasonable to incorporate the use of FDG-PET scanning to complement CT scanning in assessment of progression (particularly possible 'new' disease). New lesions on the basis of FDG-PET imaging can be identified according to the following algorithm:
 - a. Negative FDG-PET at baseline, with a positive FDG-PET at follow-up is a sign of PD based on a new lesion.
 - b. No FDG-PET at baseline and a positive FDG-PET at follow-up: If the positive FDG-PET at follow-up corresponds to a new site of disease confirmed by CT, this is PD. If the positive FDG-PET at follow-up is not confirmed as a new site of disease on CT, additional follow-up CT scans are needed to determine if there is truly progression occurring at that site (if so, the date of PD will be the date of the initial abnormal FDG-PET scan). If the positive FDG-PET at follow-up corresponds to a pre-existing site of disease on CT that is not progressing on the basis of the anatomic images, this is not PD.
 - c. FDG-PET may be used to upgrade a response to a CR in a manner similar to a biopsy in cases where a residual radiographic abnormality is thought to represent fibrosis or scarring. The use of FDG-PET in this circumstance should be prospectively described in the protocol and supported by disease-specific medical literature for the indication. However, it must be acknowledged that both approaches may lead to false positive CR due to limitations of FDG-PET and biopsy resolution/sensitivity.

Note: A 'positive' FDG-PET scan lesion means one which is FDG avid with an uptake greater than twice that of the surrounding tissue on the attenuation corrected image.

Response Criteria

Evaluation of Target Lesions

- **Complete Response (CR):** Disappearance of all target lesions. Any pathological lymph nodes (whether target or non-target) must have reduction in short axis to <10 mm (<1 cm).
- **Partial Response (PR):** At least a 30% decrease in the sum of the diameters of target lesions, taking as reference the baseline sum diameters.
- **Progressive Disease (PD):** At least a 20% increase in the sum of the diameters of target lesions, taking as reference the smallest sum on study (this includes the baseline sum if that is the smallest on study). In addition to the relative increase of 20%, the sum must also demonstrate an absolute increase of at least 5 mm (0.5 cm). (Note: the appearance of one or more new lesions is also considered progressions).
- **Stable Disease (SD):** Neither sufficient shrinkage to qualify for PR nor sufficient increase to qualify for PD, taking as reference the smallest sum diameters while on study.

Evaluation of Non-Target Lesions

- **Complete Response (CR):** Disappearance of all non-target lesions and normalization of tumor marker level. All lymph nodes must be non-pathological in size (<10 mm [<1 cm] short axis).
- Note: If tumor markers are initially above the upper normal limit, they must normalize for a patient to be considered in complete clinical response.
- **Non-CR/Non-PD:** Persistence of one or more non-target lesion(s) and/or maintenance of tumor marker level above the normal limits.
- **Progressive Disease (PD):** Appearance of one or more new lesions and/or unequivocal progression of existing non-target lesions. Unequivocal progression should not normally trump target lesion status. It must be representative of overall disease status change, not a single lesion increase.

Although a clear progression of “non-target” lesions only is exceptional, the opinion of the treating physician should prevail in such circumstances, and the progression status should be confirmed at a later time by the review panel (or Principal Investigator).

EVALUATION OF OVERALL RESPONSE CRITERIA

The best overall response is the best response recorded from the start of the treatment until disease progression/recurrence (taking as reference for progressive disease the smallest measurements recorded since the treatment started). The patient's best response assignment will depend on the achievement of both measurement and confirmation criteria. Revised Response Evaluation Criteria in Solid Tumors (RECIST) Version 1.1 ([Eisenhauer, 2009](#)) are summarized in tables within this section.

**Response According to Revised Response Evaluation Criteria in Solid Tumors
(Version 1.1): Patients with Target (\pm Non-Target) Disease**

Target Lesions	Non-Target Lesions	New Lesions	Overall Response	Best Overall Response when Confirmation is Required ^a
CR	CR	No	CR	\geq 4 weeks confirmation
CR	Non-CR/Non-PD	No	PR	\geq 4 weeks confirmation
CR	Not evaluated	No	PR	
PR	Non-CR/Non-PD/not all evaluated	No	PR	
SD	Non-CR/Non-PD/not all evaluated	No	SD	Documented at least once \geq 4 weeks from baseline
PD	Any	Yes or No	PD	no prior SD, PR, or CR
Any	PD ^a	Yes or No	PD	
Any	Any	Yes	PD	

CR=complete response; PD=progressive disease; PR=partial response; SD=stable disease.

^a In exceptional circumstances, unequivocal progression in non-target lesions may be accepted as PD.

Note: Patients with a global deterioration of health status requiring discontinuation of treatment without objective evidence of disease progression at that time should be reported as “*symptomatic deterioration*.” Every effort should be made to document the objective progression even after discontinuation of treatment.

**Response According to Revised Response Evaluation Criteria in Solid Tumors
(Version 1.1): Patients with Non-Target Disease Only**

Overall Lesion Response at Each Assessment		
Non-Target Lesions	New Lesions	Timepoint Response
CR	No	CR
Non-CR/Non-PD	No	Non-CR/Non-PD*
Not evaluated	No	NE
Unequivocal PD	Yes or No	PD
Any	Yes	PD
None	No	ND

* ‘Non-CR/Non-PD’ is preferred over ‘stable disease’ for non-target disease, since stable disease is increasingly used as an endpoint for assessment of efficacy in some trials. Therefore, to assign this category when no lesions can be measured is not advised.

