22. Has a life expectancy of less than 3 months and/or has rapidly progressing disease (e.g. tumor bleeding, uncontrolled tumor pain) in the opinion of the treating Investigator.
23. Received previous vidutolimod treatment.
24. Pregnant or breastfeeding or expecting to conceive children within the projected duration of the study, from the time of consent until at least 150 days after last dose of study treatment.
25. Sexually active men and women of childbearing potential* who are unwilling to practice highly effective contraception prior to the initial dose/start of the first treatment, during the

study, and for at least 6 months after the last dose. Highly effective contraceptive measures include:

- Stable use of combined (estrogen and progestogen containing) hormonal contraception (oral, intravaginal, transdermal) or progestogen-only hormonal contraception (oral, injectable, implantable) associated with inhibition of ovulation initiated 2 or more menstrual cycles prior to screening
- Intrauterine device (IUD); intrauterine hormone-releasing system (IUS)
- Bilateral tubal ligation/occlusion
- Vasectomized man or partner, and/or
- Sexual abstinence†, ‡.

*Postmenopausal women must be amenorrheic for at least 12 months in order not to be considered of childbearing potential. Pregnancy testing and contraception are not required for women with documented hysterectomy.

†Sexual abstinence is considered a highly effective method only if defined as refraining from heterosexual intercourse during the entire period of risk associated with the study treatments.

‡Periodic abstinence (calendar, symptothermal, post-ovulation methods), withdrawal (coitus interruptus), spermicides only, and lactational amenorrhea method (LAM) are not acceptable methods of contraception. Female condom and male condom should not be used together.

26. Had major surgeries (including complete oncologic resection) within last 4 weeks prior to enrollment, and/or have not recovered adequately from the toxicities and/or complications from the intervention. Minor surgeries (including routine resections of early stage CSCCs and BCCs that may be due to field cancerization) require a 7-day washout.

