3.8. Prohibited Treatments

Medications intended solely for supportive care are allowed (i.e. antiemetics, analgesics, megestrol acetate for anorexia).

The following concomitant medications are prohibited:

- Concurrent systemic anticancer therapy with agents other than the combination study drug therapy (vidutolimod + cemiplimab) is not allowed at any time during the study. Topical anticancer therapy agents are allowed provided they are not used for the target or non-target lesions
- Agents known to have TLR9 antagonist activity are prohibited throughout the study. The current known antagonists are chloroquine, hydroxychloroquine, and quinacrine.
- Systemic pharmacologic doses of corticosteroids > 10 mg/day of prednisone equivalent are not permitted within 15 days of study enrollment. However, corticosteroid administration is allowed in the following circumstances:
 - In the treatment of subjects with known adrenal insufficiency (see Section 4.1.1.1). Consultation with the Medical Monitor is required prior to enrollment of subjects with adrenal insufficiency.
 - Replacement doses, topical, ophthalmologic, and inhalational steroids are permitted.
 - For the management of immune-mediated toxicities and for palliation of pain or cancer related complications during study conduct. Note: Treatment on study cannot be resumed while on systemic pharmacologic doses of corticosteroids > 10 mg/day of prednisone equivalent
- Complementary medications to treat the disease under study (e.g. herbal supplements or traditional Chinese medicines).

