## 7. EFFICACY DATA

### 7.1. Description of Efficacy Data

All endpoints below will be assessed based on data reported by the investigators.

ORR is defined as the number of patients with a best overall response (BOR) of confirmed complete response (CR) or partial response (PR) divided by the total number of patients.

- Confirmation of CR or PR must occur during a subsequent evaluation at a timepoint of at least 4 weeks from the initial assessment of CR or PR.
- Best overall response of SD must have met the response SD criteria at least once  $\geq 56$  days (9 weeks for first tumor assessment –7 days window) from the first study treatment administration
- Patient(s) without baseline tumor assessment or with either unknown or missing BOR will be counted as non-responder(s).

DOR, defined as time from first confirmed response of CR or PR to first radiographic progression or death due to any cause for patients with confirmed CR or PR. In the absence of radiographic progression or death on or before the analysis cutoff date or the date of initiation of a further anti-cancer treatment, the DOR will be censored at the date of the last valid response assessment not showing progression performed on or prior to the analysis cutoff date or initiation of a further anti-cancer treatment, whichever is earlier.

DCR, defined as the percentage of patients with a BOR of CR, PR, or stable disease (SD).

TTR, defined as time from first study treatment administration to first confirmed response of CR or PR for patients with confirmed CR or PR.

PFS defined as time from the first study treatment administration to first radiographic progression or death due to any cause. The same censoring rule as DOR will be used.

OS defined as the time from first study treatment administration to death due to any cause. For patients who have not died, OS will be censored at the last date that patient is known to be alive.

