## 10. ANALYSIS OF SAFETY DATA

The analysis of safety and tolerance will be performed on the SAF .

The safety analysis will be based on the reported AEs and other safety information (clinical laboratory evaluations, vital signs and 12-lead ECG, etc.).

For safety variables, 3 observation periods are defined:

- The pre-treatment period is defined as the time from signing the screening ICF to before the first dose of study drug.
- The on-treatment period is defined as the time from first dose of study drug to the last dose of study drug plus 100 days or until the start of new systemic therapy for treatment of the patient's tumor (whichever is earlier).
- The post-treatment period is defined as the time starting 1 day after the end of on-treatment period.

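### Appendix B scores every new lesion as progression, with no exception for a histologically separate early-stage skin primary; in Cohorts A1, A2 and D such a lesion can void a response in the primary ORR

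*Protocol*

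**What the plan says.** **Response scoring (protocol Appendix B).** Under target lesions, "the appearance of one or more new lesions is also considered progressions". Under non-target lesions, PD is "Appearance of one or more new lesions and/or unequivocal progression of existing non-target lesions". The sentence that follows, asking for a change in overall disease status, limits unequivocal progression of existing non-target lesions and does not reach new ones. In both overall-response tables, a yes in the new-lesion column gives PD regardless of the other columns.

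**Response window.** Appendix B states that "The best overall response is the best response recorded from the start of the treatment until disease progression/recurrence". SAP Section 7.1 adds: "Confirmation of CR or PR must occur during a subsequent evaluation at a timepoint of at least 4 weeks" after the first CR or PR. Scans fall at W10 and every 9 weeks after that.

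**Recognition of separate skin tumours.** Protocol Section 3.6, criterion 26, sets a 7-day washout for minor surgery, including "routine resections of early stage CSCCs and BCCs that may be due to field cancerization". Criterion 9 in the same section deals with additional malignancies and exempts curatively treated basal and squamous cell skin cancers. Section 3.8 says: "Topical anticancer therapy agents are allowed provided they are not used for the target or non-target lesions".

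**Time-to-event endpoints.** Protocol Section 8.6.2 ends DOR at objectively documented recurrence or PD, or death. SAP Section 7.1 ends DOR and PFS at radiographic progression or death, and its censoring rule refers to "the date of initiation of a further anti-cancer treatment", which is not defined. SAP Section 10 closes the on-treatment safety period at the "start of new systemic therapy for treatment" of the subject's tumour.

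**The concern.** A new early-stage primary on sun-damaged skin carries no information on whether the injected and target tumours are responding. Eligibility and concomitant treatment treat such tumours as distinct from the study disease, but response scoring does not.

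Suppose a Cohort A1 subject has a large reduction in the index CSCC and a new, histologically separate early CSCC on the arm. By the written rule the subject has PD. Before confirmation this costs a response in the primary endpoint. After confirmation it ends protocol-defined DOR.

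The trial is open-label and the endpoint is investigator-assessed. An investigator who applies the rule literally and one who sets the lesion aside as unrelated would therefore score the same subject differently.

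**Working it through.** **Step 1: trace the rule.** Section 6.2 includes photographic imaging in the disease assessments, and Section 6.2.2 asks for photographs of skin lesions at a clinically relevant change, so a new skin lesion falls within the assessment. Take a subject whose target lesions first meet PR at W10. The next scheduled scan is W10 + 9 weeks = W19, which satisfies the 4-week minimum.

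| New primary first recorded | Result under the written rule |
|---|---|
| At W10 | Overall response is PD at the first assessment; the response is never recorded |
| After W10, up to W19 | PD before confirmation; not a responder in ORR |
| After W19 | ORR response stands; protocol DOR (8.6.2) ends; SAP DOR and PFS depend on whether the progression is radiographic |

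**Step 2: reproduce the plan's figures.** Protocol Table 12 (SAP Table 1) gives 25 subjects per cohort, observed thresholds of 72% (A1, D) and 24% (A2), and 90% lower bounds above 50% and 10%. The exact two-sided 90% Clopper-Pearson lower bound for x responders of n is the 0.05 quantile of Beta(x, n − x + 1).

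- A1, D: x = 0.72 × 25 = 18; Beta(18, 8) gives 53.8%, above 50%. Reproduced.
- A2: x = 0.24 × 25 = 6; Beta(6, 20) gives 11.0%, above 10%. Reproduced.

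**Step 3: remove one response.**

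| Cohort | Responders | ORR | 90% lower bound | Benchmark |
|---|---|---|---|---|
| A1, D | 18/25 | 72% | 53.8% | 50% |
| A1, D | 17/25 | 68% | 49.6% | 50% |
| A2 | 6/25 | 24% | 11.0% | 10% |
| A2 | 5/25 | 20% | 8.2% | 10% |

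The thresholds are the smallest counts that clear the benchmarks, so one voided response crosses each. On the 95% interval that will actually be reported, 18/25 to 17/25 moves the lower bound from 50.6% to 46.5%.

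**Step 4: sensitivity to an unknown rate.** The documents give no rate of new primaries and no true ORR, so both are assumptions here. Let q be the share of responses voided; then P(X ≥ 18) is taken from a binomial with n = 25 and success probability ORR × (1 − q).

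| q | True ORR 72% | True ORR 80% |
|---|---|---|
| 0% | 0.60 | 0.89 |
| 2% | 0.54 | 0.85 |
| 5% | 0.44 | 0.77 |
| 10% | 0.30 | 0.60 |

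The effect is small if q is 1–2% and large if it approaches 10%. The documents do not say where in that range the trial lies.

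**The case against.** The best counter-argument is that the gap is one of clarification. Criterion 9 lists skin cancers as additional malignancies, and Section 3.8 presupposes lesions that are neither target nor non-target, so an investigator has some textual basis for setting a separate primary aside. Appendix B also summarises a cited guideline that is not available here. This stands only in part. Appendix B is the scoring rule in the protocol, and it spells out attribution for simple cysts, effusions and FDG-PET findings. It says nothing of the kind for skin primaries, and no text tells the investigator to depart from the new-lesion rule.

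Several stronger readings are tempting, but the documents do not support them:

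- *That a later primary always shortens DOR and PFS.* SAP Section 7.1 requires radiographic progression, which a lesion seen only on examination or photograph may not be. What the text shows is a mismatch with protocol Section 8.6.2.
- *That minor resections are permitted on study.* Criterion 26 is a washout before enrollment, and Section 3.8.2 covers only palliative procedures. Only the topical permission applies on study.
- *That the protocol predicts these lesions at some rate.* It acknowledges them and gives no on-study expectation.
- *That such a lesion forces treatment to stop.* PD is a listed reason in Section 3.2, but Section 3.2.1 allows continuation after a first PD under stated conditions. Continuation does not restore the response.
- *That the SAP's censoring rule is plainly wrong.* The phrase is undefined and could be read to include a permitted topical agent. SAP Section 11.3, which moves an imputed start of post-treatment therapy to after the last dose, points towards later-line therapy. The safety window's different wording proves nothing, because it serves another purpose.
- *That 18/25 is a decision rule.* SAP Section 1.2 states no formal hypothesis, and any single misclassification would move the count equally.

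**Conclusion.** The concern holds for Cohorts A1, A2 and D. Followed as written, Appendix B turns a responder into a non-responder when a histologically separate early-stage CSCC or BCC appears before confirmation, and it ends protocol-defined DOR when one appears later. The documents do not establish the same exposure for Cohorts B1 and B2.

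The size is unknown, because no incidence is given. The illustration of one lost response (53.8% to 49.6%, and 11.0% to 8.2%) rests only on 25 subjects per cohort and exact 90% limits. The probabilities in step 4 rest on assumed rates and assumed true ORRs and should not be read as estimates.

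For DOR and PFS, the conclusion is limited to this: the protocol and SAP define progression differently and must be reconciled. The censoring phrase needs a definition; it is not a demonstrated error.

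**What to change.** 1. **Appendix B (target, non-target and overall response).** State that a new cutaneous lesion shown by histology, for example from a lesion biopsied or removed in routine care, to be a separate early-stage primary skin cancer, and not a metastasis, in-transit lesion or local extension of the study tumour, is recorded separately and is not a RECIST new lesion. Without histology it stays a new lesion. Photographic judgement alone should not suffice: in an open-label, investigator-assessed, single-arm trial, an in-transit lesion labelled as a new primary would inflate ORR.
2. **SAP Sections 7.2.1 and 13.1.** Add a sensitivity analysis of ORR with these lesions counted as PD. Section 13.1 currently lists no supportive analysis for ORR.
3. **SAP Section 7.1.** Align the DOR and PFS progression wording with protocol Section 8.6.2. This also matters because CSCC, MCC and BCC subjects without radiographically measurable disease are eligible. State that topical treatment allowed by protocol Section 3.8 is not further anti-cancer treatment for censoring.

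The cost is a few sentences and one extra table. No sample-size figure changes, and the proposal concerns endpoint scoring only; it sets no treatment rule. The downside is some remaining judgement between a new primary and an in-transit lesion. The histology requirement limits it and the sensitivity analysis shows its effect.
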